### **Motor Threshold Testing & Brain Mapping Site of Stimulation**

Stimulation intensity that will be used in iTBS will be determined by collecting each participant's motor threshold (MT) using the finger representations of the motor cortex. The consensus in the literature is that iTBS can be safely provided at 80% of active motor threshold (AMT). Since there is more within and between subject variability with AMT (e.g, different gripping strengths), relative to resting motor threshold (RMT), scientifically the RMT is preferred. There is also recent evidence that motor threshold estimates using RMT and AMT are equivalent. This means that treatment intensity, based on these two MT estimation procedures, would be equivalent, we will use RMT to estimate MT and compute treatment intensity. Thus, the standard iTBS parameters will be used in this trial to maximize safety. iTBS will be provided at 80% of RMT.

In order to determine motor threshold, a structural brain image of the participant is needed. Therefore, eligible participants will undergo an fMRI scan in order to obtain a structural brain image also referred to as the participant's 3D-MPRAGE T1 volume. This T1 image will be loaded into the Localite TMS Neural Navigator system which is a Magventure compatible and portable neuronavigational system. Based on the T1 image, the right motor cortex will be initially targeted to determine MT. Single pulse TMS will be applied to the optimal scalp location ('hot spot') to activate the abductor pollicis brevis (APB) in the hand, that functions as an abductor of the thumb, on the left hand to determine the RMT, or the lowest stimulus intensity necessary to produce MEPs of peak-to-peak amplitude  $\geq 50\mu\text{V}$  in 5 of 10 subsequent trials. MT is lowest in intrinsic hand muscles and higher in more proximal muscles. The same data will be collected on the opposite hemisphere for comparison measures. MEPs will be recorded using surface EMG electrodes. Data will be stored on the computer for offline analysis. The Magventure C-B60 coil will be used to deliver single TMS pulses for MT determination. All participants, regardless of group randomization will receive MT testing and thus will receive some stimulation. The motor threshold will be measured only at Baseline.

We will use each Veteran's MT, an indicator of cortical excitability, as the benchmark for determining iTBS intensity for each participant ( iTBS intensity will be 80% of each subject's RMT). This intensity will be maintained throughout study participation.

**iTBS** will be delivered with the Magventure MagProX100 with MagOption stimulator and Cool Coil B65. Active iTBS will be provided using active setting (A) at 80% of each Veteran's resting motor threshold. Placebo iTBS participants will not receive any stimulation as the coil will be switched to placebo (P) setting. To maintain double-blind in A and P settings, Veterans and researchers wear headphones connected to a sham noise generator.

For **APT**: 30 min of training exercises, 10 min metacognitive training, and 5 min of functional goal setting. Study-Days 2 or 3 sessions will each include novel exercises. For metacognitive training, the Veteran will be instructed on how to use strategies to self-regulate or to "think about his or her own thinking" and to self-monitor while performing an activity and efficiently allocate his or her cognitive resources. Goals will then be set to implement the strategy in the Veteran's daily life.

**iTBS** will be delivered with the Magventure MagProX100 with MagOption stimulator and Cool Coil B65. Active iTBS will be provided using active setting (A) at 80% of each Veteran's resting motor threshold. Participants randomized to active iTBS will receive stimulation at the left DLPFC at 80% RMT. 80% RMT is the intensity most commonly used and cited in the literature and has been shown to be safe. The right DLPFC will be marked in the TMS Localite

Navigation system for each participant. The navigation system will provide target guidance and will help the researcher to position the coil very precisely in reference to the participant's brain. The neuronavigation system will be used every iTBS session to ensure reproducibility and consistency at the stimulation site.

For the Optional Study: The site of stimulation will be determined by the GIMME modeling. Optimal brain target is identified through GIMME modeling, which is a directed functional connectivity modeling approach based on iterative model optimization.

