This protocol also addresses the need for pilot data to provide the empirical basis for future within-subject cross-over studies. The pilot data will inform the need to account for practice effects while estimating magnitude and duration of treatment effects from a single session of iTBS alone and a single session of iTBS + APT. As iTBS can now be tailored to each Veteran's unique neuropathology and because a single iTBS session can create a potentiated neural environment, iTBS is ideal to study alone. For healthy controls, one session of iTBS to the dorsal-lateral-prefrontal cortex (DLPFC), for example, induces gains in executive functioning. These immediate effects enhance feasibility of future cross-over studies explicating the constellation of Veteran-specific factors related to a Veteran's responses to multiple interventions. APT is ideal for pairing with iTBS, in part, because APT can be tailored to each Veteran's unique global and domain specific cognitive challenges. The tenets of metaplasticity also suggest that APT is ideal because APT is based on principles of exercise-dependent plasticity where novel training-exercises across five domains are provided to deliver stimuli of differing intensity. When APT is provided after iTBS, the provision of targeted APT stimuli during the time of iTBS enhanced plasticity is thought to regulate the plasticity ultimately optimizing cognitive gains as well as carry over of training-related gains.

Testing the scalability of an approach to feasibly and effectively tailor iTBS and APT for Veterans across stroke and TBI, advances rehabilitation research by enabling future research addressing the need for an empirical basis to tailor a broad range of cognitive rehabilitation strategies for Veterans across neurologic diagnoses. If the scientific basis for determining how-to feasibly and effectively tailor cognitive restoration interventions remain undeveloped, then Veterans with persisting cognitive impairments will continue to have diminished quality of life and sub-optimal function, ultimately relying on caregivers for performing daily activities.

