### 3.0 Objectives

**Aim 1: Elucidate merits of transdiagnostic sampling.** Within the two intervention groups (Group 1: n = 24, Active iTBS and Active iTBS + APT; Group 2: n = 24, Placebo iTBS and Placebo iTBS + APT), we expect that (1i) neurologic diagnosis (stroke, TBI) will not moderate the effect of Active iTBS or Active iTBS + APT on Maximum Cognitive Gain as assessed by the Modified Digit Span (MDS) and the Streamlined AMPS (AMPS).

**Aim 2: Obtain pilot data to inform estimation of treatment and practice effects.** We will gather pilot data regarding the magnitude and duration of treatment effects as well as MDS and AMPS practice effects. As we anticipate (2i) greater immediate gains in IADL performance (AMPS) after Active iTBS + APT when compared to Active iTBS alone, we will compare Maximum Cognitive Gains (MCG) on MDS with MCG on AMPS between the Active iTBS and Active iTBS + APT groups to determine if MCGs differ in magnitude. We will also determine if

Active iTBS + APT trend lines indicate an additive treatment effect of APT on MDS and/or AMPS. We also anticipate (2ii) some persisting treatment effects and to explicate these effects we will examine effects for Active iTBS and Active iTBS + APT in the short-term (post-pre-treatment), long-term (2 weeks after a session) and cumulatively across treatment sessions. Since the AMPS uses a unique task during each testing interval and MDS uses 1 of 6 alternate test forms, we will determine (2iii) presence and magnitude of practice effects by testing whether prior exposure to MDS or AMPS results in MDS or AMPS gains for Placebo iTBS.

**Aim 3: Explicate study attrition by perceived suitability of aspects the study design and the relationship between this perceived suitability and fatigue as well as mood.** We will test the ideas that (3i) Attrition rates do not differ by stroke and TBI groups, (3ii) Veterans across stroke and TBI have similar perceptions regarding suitability of the number and type of tests as well as number of study-days, and (3iii) perceived suitability is related to Veteran-reported fatigue and mood.

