**Figure 1. Four Step Screening Process: Summary of Exclusion Criteria by Steps**

For this within-subject placebo-controlled partially-blinded treatment protocol (Fig 2), we will enroll 48 medically stable Veterans with stabilized recovery trajectories after a stroke or a TBI and who have a homogeneous level of moderately impaired cognitive function persisting after standard rehabilitation.

An equal number of Veterans with stroke/TBI (24-stroke; 24-TBI) will be enrolled, but we will over-sample females (Figure 2). For each iTBS group to include an equal number of Veterans with stroke/TBI, Veterans will be randomly assigned by diagnostic groups, to receive Active iTBS or Placebo iTBS. To measure immediate effects (ImE), an equal number of Veterans with stroke/TBI within each iTBS group will be randomly assigned to be tested with the Modified Digit Span (MDS) or AMPS, three times at 30 min intervals. Persisting effects (PE) tests will be administered to all participants at five timepoints including prior to and after Active iTBS or Placebo iTBS and 2-weeks later prior to the 2nd intervention, where all Veterans receive APT paired with their assigned iTBS (Active iTBS + APT or Placebo iTBS + APT). The alternate ImE test is then administered three times at 30 min intervals, followed by re-administration of all PE tests. Two weeks later, all PE tests are administered a 5th time (B4). ImE and PE measures are used to define magnitude and duration of cognitive change. Randomization (SAS Proc Plan) will be managed by one un-blinded researcher who will not provide interventions or conduct testing.

**Figure 2. Study Design (ImE = Immediate Effects Tests; AMPS = AMPS or MDS = Modified Digit Span; PE = Persisting Effects Tests for all participants; Study Day-1: Obtain Covariates and Treatment preparation information; B0 = Pre-Study-Day-2; B1 = Post-Study-Day-2; After 2-Weeks B2 = Pre-Study-Day-3; B3 = Post-Study-Day-3; After 2-Weeks B4 = Study-Day 4)**

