**Study-Day 2 (4 days after Study Day 1)(~8 hours):**

- 1. PE testing battery
- 2. A single session of **Active** iTBS or **Placebo** iTBS
- 3. Randomly assigned ImE test (MDS or AMPS), administered 3-times at 30 min intervals, each interval includes 5 to 15 min of rest).
- 4. PE testing battery
- 5. Suitability ratings 1-3

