**Study-Day 3 (2 weeks after Study Day 2)(~8 hours):**

- 1. PE testing battery
- 2. Single session **Active** iTBS+ APT or **Placebo** iTBS+APT
- 3. Alternate ImE test (MDS or AMPS) three times at 30min intervals
- 4. PE testing battery
- 5. Suitability ratings 1-3

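### Aim 2i sets Day 3 (iTBS + APT) against Day 2 (iTBS alone), but the 45-minute APT block places Day 3 immediate-effect tests about 45 minutes later after stimulation, so the difference cannot be credited to APT

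*Combined protocol and SAP*

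**What the plan says.** **Order and length of the sessions.** The Study-Day 2 list in section 5.1 gives a single iTBS session followed by: "Randomly assigned ImE test (MDS or AMPS), administered 3-times at 30 min intervals, each interval includes 5 to 15 min of rest". On Study-Day 3 the session is iTBS + APT, followed by: "Alternate ImE test (MDS or AMPS) three times at 30min intervals". The text under Figure 1 confirms the order. It describes a second intervention "where all Veterans receive APT paired with their assigned iTBS", and continues: "The alternate ImE test is then administered three times at 30 min intervals".

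The Introduction (2.0) places APT after stimulation: "When APT is provided after iTBS, the provision of targeted APT stimuli during the time of iTBS enhanced plasticity". The APT paragraph in section 5.1 gives its content as "30 min of training exercises, 10 min metacognitive training, and 5 min of functional goal setting".

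**What is to be concluded.** Section 3.0 anticipates "greater immediate gains in IADL performance (AMPS) after Active iTBS + APT when compared to Active iTBS alone" and plans to compare Maximum Cognitive Gain (MCG) between those two conditions. It will also determine whether "Active iTBS + APT trend lines indicate an additive treatment effect of APT on MDS and/or AMPS".

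**Stated analysis.** Section 5.6 compares MCG by t-test within each day, Active against Placebo. It looks for the additive APT effect in the Day 3 group-by-time term, where the groups are Active iTBS + APT and Placebo iTBS + APT.

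Nothing in the documents fixes or records the time from the end of iTBS to the first immediate-effect test, or adjusts for it.

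**The concern.** Active iTBS alone exists only on Day 2 and Active iTBS + APT only on Day 3, so the Aim 2i comparison is necessarily a comparison of days. The two days differ in APT and also in how long after stimulation the outcome is sampled.

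MCG is a peak over three tests, so it depends on which part of the iTBS time course those tests cover. If the effect fades, Day 3 could look no better than Day 2 even when APT helps. If it builds, Day 3 could look better when APT does nothing. Duration of effect is one of the things Aim 2 sets out to estimate, so the plan cannot take it as flat over this interval.

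The estimates are meant to inform a future cross-over study. A wrong reading of whether APT adds to iTBS would carry into that design.

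**Working it through.** **1. Length of the APT block.** The plan prints no total. From the APT paragraph in section 5.1: 30 + 10 + 5 = 45 min.

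**2. Test times after the end of iTBS.** Let *t* be the lag from the end of the intervention to the first test. The plan gives no lag, so I assume the same *t* on both days. With the stated 30-min spacing:

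| Test | Day 2 | Day 3 | Shift |
|---|---|---|---|
| 1 | *t* | *t* + 45 | 45 min |
| 2 | *t* + 30 | *t* + 75 | 45 min |
| 3 | *t* + 60 | *t* + 105 | 45 min |

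The shift is 45/30 = 1.5 test intervals. It needs only equal lag and equal spacing on the two days, not a spacing of exactly 30 min.

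**3. What each contrast contains.** Write *S*(m) for the iTBS effect at m minutes, *A* for the effect of APT common to both arms, *I* for any iTBS-by-APT interaction, and *P* for practice and visit effects. For one outcome at the same test position, with m the Day 2 time:

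- Active Day 3 minus Active Day 2 = *A* + *I* + [*S*(m + 45) − *S*(m)] + change in *P* + carry-over from Day 2.
- Active minus Placebo on Day 3 = *S*(m + 45) + *I* + carry-over. *A* cancels because both arms receive APT.
- The Day 3 Active-minus-Placebo difference less the Day 2 one = *I* + [*S*(m + 45) − *S*(m)] + carry-over. *P* cancels if it is the same in both arms. The timing term stays and *A* is gone.

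The first contrast is the Aim 2i reading and carries the timing term directly. The second underlies the Day 3 group-by-time term in section 5.6. It has no timing imbalance between arms, but a purely additive APT effect does not appear in it at all. The trend it estimates is the later stretch of the iTBS time course plus any interaction.

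**4. Would recoding time repair the section 5.6 term?** On Day 3, minutes = *t* + 45 + 30(k − 1) for test k. This is a linear function of k. In a model linear in time, the interaction coefficient and its standard error are both divided by 30, so the test statistic does not change. Recoding matters only where the two days are set against each other.

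**5. Who is compared.** Each iTBS group has 24 Veterans, and half take each immediate-effect test: 24/2 = 12. The test switches on Day 3. For a given outcome, the cross-day contrast therefore sets about 12 Veterans against a different 12, before attrition.

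**6. Passages that leave the clock unclear.** Table 2 in section 5.5 lists 1.5 h per AMPS administration, so three take 4.5 h. The visit lists put the three tests at 30-min intervals. AMPS is the outcome named in hypothesis 2i, and its actual test times cannot be worked out for either day. Separately, the APT paragraph refers to novel exercises at Study-Day 2 or 3 sessions, although the Day 2 list contains no APT.

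**The case against.** The strongest reply is that section 5.6 does not run the comparison in dispute. Its MCG t-tests and group-by-time terms are Active versus Placebo on the same day, both arms wait through the same APT block, and no model pools the two days on one time axis. That is correct. A reader might infer that the trend-line analysis is itself biased by a misaligned clock, and the documents do not support that. The problem with that term is different: APT is common to both arms.

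A second reply is that the delay belongs to the package. APT is deliberately placed in the post-stimulation window, and testing after the whole package is a legitimate pilot estimand. This also stands, but it supports a statement about the package and not one about what APT adds.

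Third, the cross-day contrast is already weakened by visit order, two weeks' elapsed time, carry-over and different Veterans per test, so aligning minutes would not isolate APT. True, and this is why the fix limits the conclusion as well as the time variable.

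Three stronger readings are tempting and should be resisted:

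- **A bias in SD units.** One could apply an assumed half-life to the healthy-control effect in section 5.5 (g = .938). The documents give no decay rate or shape and call the magnitude in TBI and stroke unknown. Such a figure would also compare first tests, not MCG.
- **Contamination of every Day 3 versus Day 2 result.** The long-term persisting-effect assessments come two weeks after a session, where 45 min is negligible.
- **Pairing the last Day 2 test with the first Day 3 test.** On the nominal clock this is *t* + 60 against *t* + 45, so it is not a match. It also sets a third exposure against a first and breaks the fixed order of MDS forms, which section 5.5 adopts because form equivalence is untested.

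**Conclusion.** The concern holds for the cross-day reading of Aim 2i. With equal set-up lag, Day 3 immediate-effect tests fall about 45 min later after stimulation than the corresponding Day 2 tests, and nothing in the plan corrects for it. Bias arises only if the iTBS effect changes over that interval. Fading would count against APT, building would count in its favour, and a flat effect would give no timing bias. The documents do not allow a size or a direction to be stated.

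The same-day Active versus Placebo contrasts are not imbalanced in timing. The Day 3 group-by-time term still cannot show an additive APT effect, because both arms receive APT. As written, neither route supports the additive-effect conclusion that Aim 2 seeks.

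**What to change.** 1. Record the clock time of the end of iTBS and of each immediate-effect test, on both days.
2. In any model or comparison that sets Day 3 against Day 2, use actual minutes since the end of iTBS as the time variable, and keep test position or form as a separate term. If tests run exactly to schedule, minutes are fixed by day and position. Separating them then relies on the placebo arm for position effects and on an assumed shape for the time course, so the adjusted result remains descriptive.
3. State in sections 3.0 and 5.6 that the cross-day MCG difference will not be read as an additive APT effect, because it is confounded with time since stimulation, visit order and carry-over and uses different Veterans per test. State the same for the Day 3 trend term, because both arms receive APT and the term reflects a later part of the iTBS time course.
4. Reconcile the 1.5 h AMPS administration time in Table 2 with the 30-min intervals in the visit lists, and the APT paragraph's mention of Study-Day 2 with the Day 2 list.

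The cost is one time stamp per test plus one for the end of iTBS, some SAP wording, and a weaker stated conclusion for Aim 2i. No visit or test is added. Times not recorded during the visit may be impossible to recover later.

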**Study-Day 4 (2 weeks after Study-Day 3) (~2.5 hours):**

[figure not shown]
- 1. PE testing battery
- 2. Suitability rating 1-8

**Optional Study for Participants with diagnosis of TBI only- Day 5 (to occur within 2 weeks of Day 4, can occur on same day as Day 4) (~2 hours)**

- 1. Single session of Active iTBS at GIMME site of stimulation
- 2. ImE test: MDS, one time only
- 3. ImE test: AMPS, one time only

### Figure 3. Study Procedures by Study-Days 1 thru 4

ImE = Immediate Effects Tests; s-AMPS = Streamlined AMPS or MDS = Modified Digit Span; PE = Persisting Effects Tests for all participants

**Interventions.** All iTBS sessions will be **double-blinded**, but APT exercises **will not be blinded**. For **Active** iTBS and **Placebo** iTBS, the left DLPFC using the Resting Network Mapping algorithm.

**fMRI (neuroimaging)-** Functional MRI (fMRI) measures will be collected at Baseline. The fMRI measures will include structural imaging, 20 minutes of resting-state fMRI, diffusion tensor imaging (DTI) and an Arterial Spin Labelling Sequence (ASL). Participants will be in the MRI for approximately 55 minutes. fMRI scanning, for all participants, will take place at Northwestern University's CTI in the Olsen Pavilion located at [name].

Veterans will be responsible for transportation to the CTI, however parking vouchers will be provided at no cost to the participant. Parking is available at the Northwestern Memorial Hospital parking garage located across from the Olsen Pavilion. Research staff will be present on day of scan and available to provide assistance.

Scanning will take place on a Siemens Prisma 3.0 T MRI scanner equipped with a 64-channel head/neck coil. A high-resolution 3D MP-RAGE T1-weighted sagittal anatomical scan (voxel size = 0.8 mm isotropic resolution; 224 sagittal slices) will be collected for each participant. Resting state BOLD data will be collected using T2\* weighted EPI with a TR=0.5s, TE=25ms, flip angle of 48°, and 2mm isotropic voxels and a multiband factor of 8. Rest data will be collected while the subject views a fixation crosshair. The DTI data will use a two shell (64 directions per shell) acquisition with diffusion values of 1000 mm^2/sec. The acquisition will collect 1.5mm isotropic voxels with a TR=4500, TE=62ms and a multiband factor of 4, and 96 slices.

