If the 3T Skyra upgrade is not completed at time of study start up, data from each Veteran's T1 anatomical scan will be moved via encrypted USB drive to VA protected server and will be loaded into the Localite TMS Neural Navigator system which is a Magventure compatible and portable neuronavigational system. Based on the T1 image, the left motor cortex will be initially targeted and we will map 5cm anterior of the location to determine motor threshold.

If the 3T Skyra is upgraded at time of study start up, then we will locate the neural target use our Resting State Network Mapping algorithm, customized for the Northwestern imaging processing pipeline that we use in our ongoing iTBS studies.

Any finding of noncompliance, other deficiencies that substantively compromise the effectiveness of the facility's research information protection program, or suspensions or terminations will be reported to the ACOS/ACME/Research, facility Information Security Officer (ISO), and facility Privacy Officer within 5 days of becoming aware. Any loss of confidentiality falls under immediate reporting requirements and will be reported within the hour of becoming aware.

The information obtained from research analyses may be reported at scientific meetings or in other professional articles, but at no time will the Veteran, his/her family or healthcare surrogate be mentioned by name or any other identifying information.

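### The protocol marks the right DLPFC in the navigator that guides the coil, but wherever the main-study treatment site is given a side it is the left

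*Combined protocol and SAP*

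**What the plan says.** The conflict lies within one paragraph of section 5.1, under the heading on motor threshold testing and brain mapping of the stimulation site. The delivery order is: "Participants randomized to active iTBS will receive stimulation at the left DLPFC at 80% RMT". After one sentence on intensity, the paragraph continues: "The right DLPFC will be marked in the TMS Localite" navigation system, for each participant. Next comes the role of that system: "The navigation system will provide target guidance and will help the researcher to position the coil very precisely". Then its frequency of use: "The neuronavigation system will be used every iTBS session to ensure reproducibility and consistency at the stimulation site".

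The interventions paragraph of section 5.1, after the study-day schedule, gives the site for both Active and Placebo iTBS as "the left DLPFC using the Resting Network Mapping algorithm". Aim 5, in section 3.0 and again in section 5.6, looks back to the treated site as the L DLPFC and compares it with the GIMME-selected site.

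**The concern.** Read in order, the paragraph names one side for treatment and the other for the mark in the guidance system. The right DLPFC is the only location it says is marked. An operator setting up the navigator from this text would have an explicit instruction for the right side and none for the left.

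The stimulation site is the core of the intervention. If the mark were taken as the target, Active participants would be treated in a hemisphere the protocol does not name as the site. The Active versus Placebo contrasts in Aims 1 and 2 would then concern a different intervention from the one described. Aim 5 would lose its reference, because the optional Day 5 delivers only the GIMME-site session and the left DLPFC data must come from the main study.

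**Working it through.** The plan states no figure to reproduce, and sample size and power do not depend on the side of the target. The check is a comparison of every place that bears on the side, followed by a simple count.

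**Main-study treatment site**
- Section 5.1, interventions paragraph: left DLPFC, Active and Placebo.
- Section 5.1, delivery sentence: left DLPFC, Active.
- Section 3.0, Aim 5: left DLPFC, as the site already treated.
- Section 5.6, Aim 5: left DLPFC, as the comparator to the GIMME site.
- Sections 2.0 and 5.5 mention the DLPFC without a side.

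**Site marked in the navigator**
- Section 5.1: right DLPFC, for each participant. No sentence marks the left.

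**Could other text explain a right-sided mark?**
- Motor threshold testing in section 5.1 does begin on the right: "the right motor cortex will be initially targeted to determine MT". That is motor cortex, and the step sets stimulation intensity. It gives no reason to mark the right DLPFC.
- Table 5 in section 5.6 lists the right DLPFC as one of 12 GIMME regions. The optional-study site has its own paragraph and is limited to TBI, whereas the mark is made for every participant, including those with stroke.
- No right-sided control or comparison site is described.
- Section 7.0 gives two mapping routes. With the scanner upgrade: "then we will locate the neural target use our Resting State Network Mapping algorithm". Without it: "the left motor cortex will be initially targeted and we will map 5cm anterior of the location". The first names no side. The second starts on the left, although its sentence ends by giving motor threshold as the purpose. Neither supports a right DLPFC mark.

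**How many sessions could be affected**
- Floor: 0, if operators follow the left-site statements.
- Ceiling, if the mark is used as the target: 24 Active participants (sections 3.0 and 5.6) × 2 sessions (iTBS on Study-Day 2, iTBS + APT on Study-Day 3) = 48. Placebo participants receive no stimulation and add none.
- Active TBI participants, already counted in the 24: 24 TBI ÷ 2 arms = 12, since diagnoses are balanced within each iTBS group. Their sessions: 12 × 2 = 24 of the 48.
- Of those 24, only the Study-Day 2 sessions are iTBS alone: 12 × 1 = 12. These match Aim 5's single-session comparison most closely.

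**The case against.** The strongest reply is that this is a typographical slip whose intended meaning can be recovered from the same paragraph. The delivery sentence says left, the interventions paragraph derives a left target from the mapping algorithm, and Aim 5 says left twice. A right-sided session would require an operator to override all of these. On that view the point is editorial, and the count of 48 is a bare ceiling: nothing in the documents supports any particular value above zero.

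Much of this stands. A slip is the likeliest cause, and the range does not estimate how many sessions would go wrong. Two narrower criticisms are also fair. The fallback in section 7.0 is worded for motor threshold, so it is weak corroboration of a left target. The 24 Active TBI sessions include 12 combined with APT.

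None of this removes the conflict. The interventions sentence that gives the left target has no verb, and the mapping routes sit in the privacy section. The one complete sentence on what is marked in the navigator carries the unexplained side. Because that sentence governs coil placement, it should not be left for the operator to resolve.

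**Conclusion.** The concern holds. The protocol orders treatment at the left DLPFC and marks the right DLPFC in the system that guides the coil, with no stated reason. That the text is inconsistent is certain; the effect on the trial is conditional. Between 0 and 48 active sessions could be misdirected. Within that ceiling, up to 12 Active TBI participants are the only possible source of the left DLPFC reference for Aim 5. The ceiling assumes full enrolment of 24 Active participants, both sessions delivered, and the mark used as the target every time. The documents do not show that wrong-side delivery has occurred or is likely. The point should be fixed because the sentence is operative and the correction is nearly free.

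**What to change.** In the iTBS paragraph of section 5.1, change right to left in the sentence on marking the DLPFC in the navigation system. If a right-sided mark is intended for some other purpose, keep it, state that purpose, and add a sentence confirming that the left DLPFC is marked as the treatment target for Study-Days 2 and 3. The cost is a one-word protocol correction or a short addition. Sample size, randomization and analysis are unchanged.
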